#### 7.1.2 *Participant Exclusion Criteria*

##### Exclusion criteria for cohort participants

Men and women who meet any of the following criteria are ineligible for inclusion as a cohort participants:

- Not competent to provide written informed consent
- Unwilling or unable to provide a blood sample

## 7.2 Recruitment Process

We will enroll cohorts of participants at each of the 12 study sites, with a target enrollment of 60 participants at each site (720 overall). Data from the cohorts will be used to draw inferences about the acceptability and effectiveness of the ICV. We have taken steps to minimize selection or follow-up bias between the ICV and cohort activities. First, cohorts will be recruited prior to randomization (so research staff will not know which sites will receive the intervention when they are recruiting the cohorts). Second, the cohorts will be recruited and followed by a dedicated research team on a research van that is separate from the mobile SSP and the ICV. This separation of research from the ICV will minimize the risk that research activities affect ICV service utilization. The goal will be to recruit PWID clients of the mobile SSP and other PWID in the neighborhood who might access services on the ICV.

We will use a dedicated research van to recruit individuals at each of the neighborhood sites (near cross-street locations where the Baltimore City mobile SSP makes regular stops). The research van will accompany the SSP van to sites where it is actively recruiting cohorts. We will post study recruitment flyers on the SSP van and staff on the van will refer interested clients to the research van. Additionally, research staff will encourage word-of-mouth referrals from participants.

## 7.3 Participant Retention

Our experienced team is well aware of the challenges of PWID study retention. Once a participant enrolls in the cohort study, the research team will make every effort to retain him/her for the full study period (~14 months). Study site staff will develop and implement local standard operating procedures to target this goal. Components of such procedures include:

- Thorough explanation of the study visit schedule and procedural requirements during the informed consent process and re-emphasis at each study visit.
- An experienced van research team with a lifelong knowledge of Baltimore City.
- Collection of detailed and multifaceted locator information at the baseline visit, and active review and updating of this information at each subsequent visit.
- Use of mapping techniques to establish the location of participant residences and other locator venues.
- Visit reminder calls and letters.
- Reimbursed “check-in” phone contacts between the scheduled study visits (i.e., ~3 months and ~9 months)
- Regular communication with the PWID community at large to increase awareness about follow-up and the research van’s current and future location.
- Use the van to visit participants’ last known residence (“knocking on doors”).

## 8. INTERVENTIONS

Study sites (clusters) will be randomly allocated to either the ICV intervention or to the control condition.

**Table 1. Comparison of services with the mobile SSP alone (control) and the SSP combined with the ICV (intervention).**

Type of service	SSP (control)	ICV intervention
Risk reduction		
SSP	Confidential (ID-based) SSP using hybrid exchange/distributive model	Same
Overdose prevention /response	SSP program leads city-wide initiative to train and provide naloxone overdose kits to PWID, their friends, and family	Same, although ICV will provide increased opportunities for naloxone kit training and distribution
PrEP	Refer to PrEP program offered at BCHD clinics	Onsite provision of PrEP education, clinical /lab screening for PrEP eligibility, PrEP prescription, and monitoring
HIV care cascade		
HIV testing	Free (non-rapid) HIV and syphilis testing offered on the van once or twice a year	Free rapid HIV testing offered daily
Linkage to HIV care	No routine service	Intervention team tracks care cascade using Data to Care program, peer navigators link clients to care.
ART adherence /viral suppression	No routine service on mobile SSP.	ICV team communicates with HIV treatment providers in city, tracks patients who have lapsed with ART prescription fills, on-site case management to address barriers, laboratory testing on van to assist clinic, ART refills provided
Substance abuse treatment	Referral to buprenorphine- or methadone-based MOUD with dedicated slots for SSP clients	Low-barrier, same-day prescription of buprenorphine, with transition community-based MOUD
Additional PWID services		
HCV care cascade	Referral to BCHD clinics or elsewhere for testing, disease staging, and treatment	HCV antibody and HCV RNA testing on ICV, initiate HCV treatment on ICV with case management support. Referral for advanced liver disease.
Wound care	Referral to primary care provider or emergency department	Wound care-certified NP offers acute and chronic wound care management on the van, with referral for specialized treatment 

## 8.1 Control Condition

Control (usual care) sites will receive services currently provided by 2 Baltimore City Health Department mobile SSPs. Together, these vans visit ~15 sites around Baltimore City each week (busy sites are visited more than once per week). In 2015, the SSP had 16,164 visits by 4512 unduplicated clients, and distributed 1,071,927 clean syringes. In addition to needle/syringe services, the SSP vans offers outreach HIV and syphilis testing (not rapid testing) approximately twice a year (the SSP van is not normally staffed for phlebotomy). Second, the SSP provides opioid overdose reversal training and distributes naloxone nasal spray kits directly to clients. Third, the SSP can refer clients to opioid agonist treatment programs that have dedicated treatment slots for SSP referrals. For other services (HIV management, PrEP, HCV testing and treatment evaluation, wound care, etc.) the SSP provides no direct services.

## 8.2 ICV Intervention

The integrated care van (ICV) is a medically-staffed, mobile health facility that will provide PWID-oriented medical services and case management. ICV services will include 1) linkage, support, and medical management for HIV-positive clients, 2)

screening and initiation of pre-exposure prophylaxis (PrEP) for high-risk HIV-negative PWID, 3) low-barrier initiation of buprenorphine/naloxone and transfer to community-based medication assisted treatment, 4) HCV testing, liver disease staging, and HCV treatment with direct acting agents, and 5) wound care. The ICV will visit different neighborhood stops/sites according to an established weekly schedule. The ICV is a structural intervention that will provide the staff, physical space, equipment, and information technology to bring a package of evidence-based biomedical services to the outermost public health-PWID interface. The ICV is a 40-foot Freightliner that includes 2 patient exam rooms, a waiting space, a phlebotomy/laboratory area, and a bathroom. Electricity is provided by an on-board generator. The ICV will be staffed by BCHD employees, including one or two medical providers (physicians and mid-level practitioners), a case manager, and a phlebotomist/driver. The clinical staff are experienced in HIV treatment, PrEP screening and management, HCV treatment, buprenorphine (with Drug Enforcement Agency waiver), and wound care. Under the auspices of the BCHD, the ICV will provide services to anyone who visits the unit.

## 9. STUDY PROCEDURES/EVALUATIONS

### 9.1 Clinical Evaluations and Procedures

Eligible participants who meet inclusion criteria and provide written informed consent will be enrolled to the local cohort. Cohort participants will complete a baseline study visit, most often on the day of screening, and will be asked to complete follow-up visits at 7 months and 14 months, for a total of 3 study visits. Study visits will include the following evaluations:

- Biometric capture (iris scan) to assure identity
- Blood draw and urine sample
- Collection of contact and locator information
- Interviewer-administered survey covering the following domains
  - Demographics
  - Quality of life
  - Engagement/experience with HIV, HCV, PWID services
  - Alcohol and drug use
  - Injection- and sex-related risk behaviors
  - Depression symptoms
  - Health care utilization

### 9.2 Laboratory Evaluations

**Table 2. Laboratory testing for cohort participants**

Test	CLIA status	Visits measured	Participants included	
			HIV-negative	HIV-positive
bioLytical Laboratory INSTI HIV-1/HIV-2 point-of-care Rapid HIV test	Waived	SCR	•	•
CD4 cell count, flow cytometry, JHH	Certified	V00		•
HIV-1 antibody test	Certified	V14	•	
HIV RNA	Certified	V00, V07, V14		•

**Table 2. Laboratory testing for cohort participants**

Test	CLIA status	Visits measured	Participants included	
			HIV-negative	HIV-positive
Tenofovir diphosphate concentration in peripheral blood mononuclear cells	Non-certified	V00, V07, V14 (among subset reporting linkage to PrEP)	•	
Hepatitis C virus (HCV) serology	Certified	V00	•	•
HCV RNA	Certified	V00 & V14 (in HCV seropositive only)	•	•
Urine drug screening, high resolution accurate mass spectrometry	Certified	V00, V07, V14	•	•

SCR, screening; V00, baseline visit, V07, 7-month visit; V14, 14-month visit

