#### **5.2 Secondary Objectives:**

- To determine if the ICV intervention improves the HIV care continuum (among HIV-positive participants), compared with the control condition
- To determine if the ICV intervention increases HIV testing rates (among HIV-negative participants), compared with the control condition.
- To determine if the ICV intervention improves the PrEP continuum (among HIV-negative participants), compared with the control condition.
- To determine if the ICV intervention improves the HCV care continuum (among HCV-positive participants), compared with the control condition.
- To determine if the ICV intervention increases HCV testing rates (among HCV-negative participants), compared with the control condition.
- To determine if the ICV intervention increases use of MOUD (among all participants), compared with the control condition.
- To determine if the ICV intervention increases use of SSP (among all participants), compared with the control condition.
- To determine if the ICV intervention increases possession of a naloxone overdose kit (among all participants), compared with the control condition.
- To determine if the ICV intervention reduces injection drug use (among all participants), compared with the control condition.
- To determine if the ICV intervention reduces recent drug use (among all participants), compared with the control condition.
- To determine if the ICV intervention reduces sharing of drug paraphernalia (among all participants), compared with the control condition.

- To determine if the ICV intervention reduces non-fatal drug overdoses (among all participants), compared with the control condition.
- To determine if the ICV intervention reduces emergency department use (among all participants), compared with the control condition.
- To determine if the ICV intervention reduces HIV seroconversion (among HIV-negative participants), compared with the control condition.
- To determine if the ICV intervention reduces HCV seroconversion (among HCV-negative participants), compared with the control condition.
- To determine if the ICV intervention decreases mortality (among all participants), compared with the control condition.

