### **9.2.2 Total Blood Volume**

We will draw a blood volume of 25 cc at the baseline, 7 month, and 14-month visits. The maximum amount of blood drawn over an 8-week period is 25 cc.

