## 14. APPENDIX

**Table. Rubric for composite PWID score (service access, risk behaviors, adverse outcomes)**

Score component	Denominator	Category definitions
Service access		
HIV care continuum	HIV positive	0 – Suppressed (HIV RNA <200 c/mL) 1 – Not suppressed, and either i) took ARVs in prior 30 days (self-report) OR ii) had visit with HIV provider in prior 6 months 2 – Not suppressed AND did not take ART in prior 30 days AND did not have visit with HIV provider in prior 6 months (includes those unaware of HIV+ status) at the visit
HIV testing	HIV negative	0 – Had HIV test in past 6 months 1 – Did not have HIV test in past 6 months
PrEP continuum	HIV negative	0 – Used PrEP in prior 6 months (self-report) 1 – Did not use PrEP in prior 6 months
HCV care continuum	HCV positive i. all Ab(+) + RNA(+) or ii. Ab(+) + RNA(-) + treated	0 – HCV treatment history (self-report) and HCV RNA suppressed (<15) 1 – Not suppressed and either treated for HCV OR evaluated by HCV provider in prior 6 months 2 - Not suppressed AND not treated for HCV in prior 6 months AND not evaluated by HCV provider in prior 6 months.
HCV testing	HCV negative i. Ab(-) or ii. Ab(+) + RNA(-) + never treated	0 – Had HCV test in past 6 months 1 – Did not have HCV test in past 6 months
MOUD use	All	0 – Used MOUD in past 6 months 1 – Did not use MOUD in past 6 months
SSP use	Injected in prior 6 months	0 – Used SSP in past 6 months 1 – Did not use SSP in past 6 months
Available naloxone kit	All	0 – Has naloxone kit on person or where drugs used 1 – Does not have accessible naloxone kit
Risk behaviors		
Injection drug use	All	0 – No injection drug use in prior 6 months (self-report) 1 – Injection drug use in prior 6 months
Recent drug use	All	0 – Urine drug test negative for drugs of concern (*see footnote) 1 – Urine drug test positive for one or more drugs of concern (*see footnote)
Sharing injecting equipment	All	0 – No sharing syringe/works OR not using/injecting in prior 6 months 1 – Sharing works (cotton/cooker) only in prior 6 months 2 – Sharing needle/syringe in prior 6 months
Adverse outcomes		

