**Table. Rubric for composite PWID score (service access, risk behaviors, adverse outcomes)**

Score component	Denominator	Category definitions
Non-fatal overdose	All	0 – No overdose in prior 6 months 1 – One or more overdose in prior 6 months
Emergency department use	All	0 – No ED visits in past 6 months 1 - One or more ED visits in past 6 months (Self-report, supplemented by CRISP)
Clinical status change assessed at follow-up only		
HIV seroconversion	HIV negative	0 – No HIV seroconversion 2 - HIV seroconversion occurring between baseline and follow-up
HCV seroconversion	HCV negative	0 – No HCV seroconversion 1 - HCV seroconversion occurring between baseline and follow-up
Death	All	0 – Alive 15 (maximum points) – Confirmed death during follow-up

\*Includes fentanyl (or metabolite), heroin (morphine or 6MAM), cocaine (or metabolite), amphetamine

Revised scoring system 25 OCT 2021

HIV status	HCV status	Maximum score
-	-	15
-	+	15
+	-	13
+	+	13

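### HCV seroconversion is a secondary endpoint, but Table 2 schedules no follow-up HCV test for the antibody-negative participants who could seroconvert

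*Combined protocol and SAP*

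**What the plan says.** **Endpoint.** Section 5.2 sets the objective: "To determine if the ICV intervention reduces HCV seroconversion (among HCV-negative participants), compared with the control condition". Section 12.2.2 lists HCV seroconversion as a secondary endpoint. The Appendix rubric, in its block assessed only at follow-up, gives 1 point for "HCV seroconversion occurring between baseline and follow-up", with HCV-negative participants as the denominator. The HCV testing row defines HCV negative as antibody-negative, or as "Ab(+) + RNA(-) + never treated".

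**Tests.** In Table 2 the row "Hepatitis C virus (HCV) serology" carries V00 alone. The HCV RNA row reads "V00 & V14 (in HCV seropositive only". The key is "V00, baseline visit, V07, 7-month visit; V14, 14-month visit". The HIV counterpart differs: HIV-negative participants have an HIV-1 antibody test at V14.

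**Blood and other sources.** Section 9.2.2 states: "We will draw a blood volume of 25 cc at the baseline, 7 month, and 14-month visits". Section 9.3.3 lists a blood draw at follow-up without naming assays. Section 12.2 says endpoints rest on laboratory tests, interviews and external sources, among them CRISP treatment episodes and the National Death Index.

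**Timing.** Section 9.3.4 reports enrollment from July 2018 to August 2019. When the pandemic closed the study, 7-month visits were complete at all 12 sites and 14-month visits at 4. Telephone visits without laboratory tests followed, and in-person visits resumed in July 2021. Primary analyses use baseline and 7 months.

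**The concern.** Seroconversion means moving from antibody-negative to antibody-positive, so it needs a second antibody test in people who began negative. Table 2 provides none. An analyst following the plan would have to leave the endpoint empty, score untested people 0 as if they had been shown not to seroconvert, or fill the gap with results obtained outside the study visits. The second choice produces a null finding from absent data. The third makes detection depend on how often people are tested elsewhere. Table 1 has the ICV testing for HCV on board while control sites refer, and more HCV testing is itself a study objective, so detection could differ by arm.

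The gap is not only a consequence of moving the primary analysis to 7 months. HIV seroconversion has a scheduled test at V14. HCV seroconversion has none at any follow-up visit.

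**Working it through.** **1. Scheduled HCV tests, by baseline status (Table 2)**

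| Baseline status | V00 | V07 | V14 |
|---|---|---|---|
| Antibody-negative | serology | none | none |
| Antibody-positive | serology, RNA | none | RNA |

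The restriction to seropositive people might apply to V14 alone or to both RNA visits; the follow-up columns are the same either way. It must also refer to baseline serostatus, because no later antibody test exists to update it. Follow-up HCV tests for people able to seroconvert: 0 at V07 and 0 at V14.

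**2. Composite maxima**

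The plan's own figures are reproduced first.

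- Items common to everyone: MOUD 1 + SSP 1 + naloxone 1 + injection 1 + urine 1 + sharing 2 + overdose 1 + ED 1 = 9.
- HIV-negative: testing 1 + PrEP 1 + seroconversion 2 = 4. HIV-positive: care continuum 2.
- HCV-negative: testing 1 + seroconversion 1 = 2. HCV-positive: care continuum 2.

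Totals by HIV/HCV status (−/−, −/+, +/−, +/+): 9+4+2 = 15, 9+4+2 = 15, 9+2+2 = 13, 9+2+2 = 13. These match the Appendix.

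Removing the HCV seroconversion point, which no scheduled test can award, gives 14/15/12/13 at V14 for survivors. At V07 the HIV antibody test is also absent, so HIV-negative participants lose a further 2 points: 12/13/12/13. (The V07 figures count the HCV care item in full, although its RNA is not scheduled at V07 either.)

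**3. How much testing could recover**

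The 80% retention is from section 12.4. The documents give neither the antibody-negative share nor incidence, so I assume 30–50% and 5–15 per 100 person-years. Fourteen months is 14/12 = 1.17 years and seven is 7/12 = 0.583.

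- V14, the 4 sites completed before the shutdown: 4 × 60 = 240 enrolled. Testable: 240 × 0.30 × 0.8 = 58 to 240 × 0.50 × 0.8 = 96. Events: 58 × 0.05 × 1.17 = 3 to 96 × 0.15 × 1.17 = 17.
- V07, all 12 sites, if blood was kept: 720 × 0.30 × 0.8 = 173 to 720 × 0.50 × 0.8 = 288. Events: 173 × 0.05 × 0.583 = 5 to 288 × 0.15 × 0.583 = 25.

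**4. Resumed visits**

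July 2021 is 23 months after August 2019 and 36 months after July 2018. In-person visits at resumption therefore fall about 23–36 months after baseline, following a suspension of the ICV that lasted many months.

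**The case against.** **Some of the HCV-negative group is tested.** A reader might infer that nobody in that group has a follow-up test. That goes too far. The rubric includes antibody-positive, RNA-negative, never-treated people, and they get RNA at V14. A new positive RNA would be observable, and the plan never defines seroconversion by assay. This objection stands as a limit on the point. It does not remove it: these people are already antibody-positive, so what V14 shows is new viraemia, and antibody-negative participants remain untested. It also exposes a second fault, since the denominator contains people who cannot seroconvert.

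**Section 12.2 allows interviews and external data.** It does, and the list of external sources is not closed. What CRISP holds on HCV serology is not in the documents, so one cannot say that no information exists anywhere. But no rule derives HCV seroconversion from these sources.

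**Bias against the ICV.** A reader might infer that the ICV would appear to cause infections by a calculable amount. The direction is plausible if outside tests are used and untested people count as negative. The documents give no testing rates by arm and do not propose that step, so no size can be attached.

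**Little is lost.** This is one of 16 secondary endpoints. Section 12.7.1 gives it no analysis of its own, and no power figure depends on it. If the 4 completed sites are the first recruitment set of two pairs (section 12.5), V14 offers 2 clusters against 2. All of this limits what the repair can deliver; the mismatch between Table 2 and the endpoint list remains.

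**Conclusion.** Table 2 contradicts sections 5.2 and 12.2.2 and the Appendix. Participants antibody-negative at baseline have no scheduled HCV test at V07 or V14, so neither the secondary endpoint nor its rubric point can be measured from study tests at any visit. This follows from the schedule alone and needs no assumption.

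The effect on the composite is one unattainable point for HCV-negative participants. The documents do not support the stronger inference that this invalidates the primary analysis.

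The recoverable information is small. A reader might multiply through all 720 participants at 14 months, but section 9.3.4 rules that out: only 4 of 12 sites had completed V14 before the shutdown, and telephone visits had no laboratory tests. The V14 range of 3–17 events rests on the assumed antibody-negative share and incidence, and on specimens being available, which the documents do not state.

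**What to change.** - In Table 2, add HCV antibody with reflex RNA at follow-up for baseline antibody-negative participants. Run it on blood already drawn where specimens exist: V07 at all sites, and V14 where visits were in person.
- Restrict the seroconversion denominator to antibody-negative participants, and define the endpoint from study tests only. If new viraemia in antibody-positive, RNA-negative, never-treated people is of interest, name it separately.
- State that untested participants are missing, not 0, and that community, van and self-reported results are not used.
- Report tests from visits after resumption in July 2021 separately, as later follow-up of about 23–36 months, not as V14.
- If no specimens exist, say in 5.2, 12.2.2 and the Appendix that HCV seroconversion was not assessed. Remove its point from the composite and amend the maxima. An open statement is better than silent deletion, because this version is dated April 2022, after enrollment and the 7-month visits.

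The cost is one antibody assay per antibody-negative participant and visit with blood available, plus RNA for any positives. On the assumptions above that is about 58–96 assays at V14 in the 4 completed sites, and up to 173–288 at V07 if all sites kept specimens. Testing stored blood needs no new visit or draw. The main drawback is that few events are expected, so the comparison will be imprecise and should be presented as such.

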### **9.2.1 Biohazard Containment**

As the transmission of HIV and other blood-borne pathogens can occur through contact with contaminated needles, blood, blood products and body fluids, appropriate blood and secretion precautions will be employed by all personnel in the drawing of blood and shipping and handling of all specimens for this study, as currently recommended by the United States Centers for Disease Control and Prevention. All infectious specimens will be transported in accordance with United States regulations (42 CFR 72).

